5.4.5.7. Procedures for Other Immune-Mediated Adverse Reactions, Including Ocular Manifestations

All study treatment should be permanently discontinued for severe immune-mediated adverse reactions. Systemic corticosteroids treatment should be initiated at a dose of 1 to 2 mg/kg per day of prednisone or equivalent for severe immune-mediated adverse reactions.

Corticosteroid eye drops should be administered to subjects who develop uveitis, iritis, or episcleritis. All study treatment should be permanently discontinued for immune-mediated ocular disease that is unresponsive to local immunosuppressive therapy.

For additional management and follow-up guidance for renal immune events see [Appendix B](#).

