Grade 3	
Withhold study treatment until AE improves to Grade \leq 1.
 
Discontinue if unable to reduce corticosteroid dose to < 10 mg/day of prednisone or equivalent within 6 weeks of toxicity.
	
Any restart of study treatment must be discussed with medical monitor. Epacadostat should be reduced 1 dose level after AE has resolved to Grade \leq 1.
	
Systemic corticosteroids are indicated in addition to appropriate symptomatic treatment. May use 1 to 2 mg/kg prednisone or equivalent per day.
 
Steroid taper should be considered once symptoms improve to \leq Grade 1 and tapered over at least 4 weeks in most cases.

Grade 4	Discontinue study treatment. ^a	Not applicable. Any exceptions require medical monitor approval.	
Systemic corticosteroids are indicated in addition to appropriate symptomatic treatment. May use 1 to 2 mg/kg prednisone or equivalent per day.
 
Steroid taper should be considered once symptoms improve to \leq Grade 1 and tapered over at least 4 weeks in most cases.

^a See Section 5.4.8 for study treatment withdrawal criteria.

Note: Detailed management guidelines for specific irAEs can be found in Sections 5.4.5.1 through 5.4.5.7.

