5.4.5.4. Procedures for Immune-Mediated Dermatitis

Monitor subjects for signs and symptoms of dermatitis such as rash and pruritus. Unless an alternate etiology has been identified, signs or symptoms of dermatitis should be considered immune mediated. Recommendations for management of dermatitis are shown in [Table 14](#) as well as additional information for management and follow-up in [Appendix B](#).

Table 14: Recommended Approach for Handling Dermatitis

irAE	Withhold/Discontinue Nivolumab and Epacadostat	Guidance for Restarting Study Treatment	Supportive Care
Grade 1	No action.	Not applicable.	For mild to moderate dermatitis, such as localized rash and pruritus, treat symptomatically. Administer topical or systemic corticosteroids if there is no improvement of symptoms within 1 week.
Grade 2	No action.	Not applicable.	For mild to moderate dermatitis, such as localized rash and pruritus, treat symptomatically. Administer topical or systemic corticosteroids if there is no improvement of symptoms within 1 week.
Grades 3 and 4	Withhold study treatment in subjects with moderate to severe signs and symptoms of rash. Permanently discontinue study treatment in subjects with Stevens-Johnson syndrome, toxic epidermal necrolysis, or rash complicated by full thickness dermal ulceration or by necrotic, bullous, or hemorrhagic manifestations.	If AE resolves to baseline within 4 weeks, subject may restart at the same dose and schedule for both epacadostat and nivolumab and ipilimumab (Treatment Group A) or lirilumab (Treatment Group B). For an AE that resolves to \leq Grade 1 between 4 and 6 after onset, epacadostat should be reduced 1 dose level, but nivolumab and ipilimumab (Treatment Group A) or lirilumab (Treatment Group B) may be restarted at the same dose and schedule. If AE does not resolve to \leq Grade 1 within 6 weeks, all study treatment should be discontinued or discussed with medical monitor.	Administer systemic corticosteroids at a dose of 1 to 2 mg/kg per day of prednisone or equivalent. When dermatitis is controlled, corticosteroid tapering should occur over a period of at least 1 month.

Note: See [Appendix B](#) for additional guidance regarding management of dermatitis.

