Grade 3	Withhold or discontinue study treatment.	If AE resolves or is controlled within 4 weeks, subject may restart at the same dose and schedule for epacadostat, nivolumab and ipilimumab (Treatment Group A) or lirilumab (Treatment Group B). For an AE that does not resolve within 4 weeks, epacadostat should be reduced 1 dose level, but nivolumab and ipilimumab (Treatment Group A) or lirilumab (Treatment Group B) may be restarted at the same dose and schedule. If AE does not resolve within 6 weeks, study treatment should be discontinued.	Consider initiating systemic corticosteroids treatment at a dose of 1 to 2 mg/kg per day of prednisone or equivalent, and initiate appropriate hormone replacement therapy.
Grade 4	Discontinue study treatment.	Not applicable. Any exceptions require medical monitor approval.	Consider initiation of systemic corticosteroids at a dose of 1 to 2 mg/kg per day of prednisone or equivalent, and initiate appropriate hormone replacement therapy.

Note: See [Appendix B](#) for additional guidance regarding management of endocrinopathies.

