5.4.8. Criteria for Permanent Discontinuation of Study Treatment

The occurrence of unacceptable toxicity not caused by the underlying malignancy will be presumed to be related to study treatment and will require that the study drug be permanently discontinued. Unacceptable toxicity is defined as follows:

- Grade 4 or life-threatening AEs, except with approval from the medical monitor.
- Toxicity requiring more than 2 dose reductions of epacadostat, or dose reductions below 25 mg BID.
- \geq Grade 2 ocular irAE.
- Occurrence of an AE that is related to treatment with the study drug that, in the judgment of the investigator or the sponsor's medical monitor, compromises the subject's ability to continue study-specific procedures or is considered to not be in the subject's best interest.
- Persistent AE requiring a delay of therapy for more than 4 weeks (28 days) unless a greater delay has been approved by the sponsor.

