8.1.2. Reporting

Adverse events that begin or worsen after informed consent should be recorded on the Adverse Events form of the eCRF. Conditions that were already present at the time of informed consent should be recorded on the Medical History form in the eCRF. Monitoring for the occurrence of new AEs should be continued for at least 100 days after the last dose of study treatment for Treatment Group A, and 150 after the last dose of study treatment for Treatment Group B. Adverse events (including laboratory abnormalities that constitute AEs) should be described using a diagnosis whenever possible rather than by individual underlying signs and symptoms.

The term "disease progression" should be recorded as an AE/SAE only if there are no other identifiable AEs/SAEs associated with the disease progression at the time of reporting. For events associated with disease progression, the relevant signs and symptoms should be reported using a diagnosis whenever possible rather than individual underlying signs and symptoms. When a clear diagnosis cannot be identified, each sign or symptom should be reported as a separate AE. If the events resulting from disease progression meet the criteria for an SAE (eg, resulted in hospitalization, a life-threatening event, or death), the specific event(s) should be reported as an SAE(s) as described in Section 8.3.2. In both cases (ie, AEs or SAEs related to disease progression), it should be indicated that each event (reported as a diagnosis or as signs and symptoms) is related to disease progression on the Adverse Events form of the eCRF.

The severity of AEs will be assessed using CTCAE v4.03 Grades 1 through 5. If an event is not classified by CTCAE, the severity of the AE will be graded according to the scale below to estimate the grade of severity:

Grade 1	Mild; asymptomatic or mild symptoms; clinical or diagnostic observations only; intervention not indicated.
Grade 2	Moderate; minimal, local, or noninvasive intervention indicated; limiting age-appropriate activities of daily living.
Grade 3	Severe or medically significant but not immediately life-threatening; hospitalization or prolongation of hospitalization indicated; disabling; limiting self-care activities of daily living.
Grade 4	Life-threatening consequences; urgent intervention indicated.
Grade 5	Death due to AE

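### Two immune-related AE rules contradict other current text: Section 5.4.5.7 against Table 10 for severe reactions with no table of their own, and Table 14 against Section 5.4.8 for Grade 4 dermatitis

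*Combined protocol and SAP*

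**What the plan says.** The protocol gives instructions for immune-related AEs at three levels: general tables, organ-specific tables, and criteria for permanent discontinuation.

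- **Section 5.4.5.7**, headed "5.4.5.7. Procedures for Other Immune-Mediated Adverse Reactions, Including Ocular Manifestations", says: "All study treatment should be permanently discontinued for severe immune-mediated adverse reactions". It names no grade and no route back to treatment.
- **Table 10** (Section 5.4.5), Grade 3: withhold until Grade 1 or better, then "Any restart of study treatment must be discussed with medical monitor. Epacadostat should be reduced 1 dose level after AE has resolved". At Grade 4: discontinue, with exceptions only by medical-monitor approval.
- **Table 9** (Section 5.4.4.2) labels Grade 3 as severe, holds treatment and restarts epacadostat one level lower. At Grade 4 it requires permanent discontinuation unless the medical monitor approves.
- **Table 14** (Section 5.4.5.4), one row for dermatitis of Grades 3 and 4: withhold, and "If AE resolves to baseline within 4 weeks, subject may restart at the same dose and schedule for both epacadostat and nivolumab and ipilimumab" (or lirilumab in Group B). Immediate permanent discontinuation is reserved for listed skin forms.
- **Table 16** (Section 5.4.5.6), Grade 3 endocrinopathy: "If AE resolves or is controlled within 4 weeks, subject may restart at the same dose and schedule for epacadostat" and the antibodies. Its Grade 4 row discontinues treatment.
- **Section 5.4.8** lists as unacceptable toxicity "Grade 4 or life-threatening AEs, except with approval from the medical monitor". Section 5.5.1 makes withdrawal from study treatment mandatory for unacceptable toxicity.

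**The concern.** An investigator with a subject in front of them should reach the same action from any section of the protocol. For a severe reaction with no table of its own, one section ends all treatment and another provides for a restart. For Grade 4 dermatitis, one table permits a full-dose restart and the discontinuation criteria require withdrawal unless an approval is obtained that the table does not mention.

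Enrollment is closed, but Appendix F says Amendment 2 exists partly to guide subjects who continue on treatment, so these instructions are still in use for Treatment Group A. There is also a reporting consequence. Section 9.4.2.5 summarizes immune-related AEs leading to interruption, dose reduction or discontinuation. If sites follow different sections, those counts mix the toxicity of the regimen with the choice of section. Section 9.4 limits summary tables to selected safety analyses and does not say whether this one is kept, but listings would carry the same ambiguity.

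**Working it through.** No arithmetic applies. The check sets the current passages side by side by grade and type of event.

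**Step 1. What *severe* means in 5.4.5.7.** The section does not say. Table 9 attaches the word to Grade 3 and calls Grade 4 life-threatening. The scale in Section 8.1.2 describes Grade 3 as "Severe or medically significant but not immediately life-threatening", but that scale applies only to events CTCAE does not classify, so it is supporting evidence. The discontinuation column of Table 9's Grade 4 row speaks of severe as well as life-threatening events, which blurs the term.

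**Step 2. Reactions with no table of their own.**

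| Reading of *severe* | Section 5.4.5.7 | Table 10 | Result |
|---|---|---|---|
| Grade 3 and above | Permanent stop, no exception | Grade 3: withhold, restart possible with epacadostat reduced, after discussion with the medical monitor | Contradiction |
| Grade 4 only | Permanent stop, no exception | Grade 4: stop unless the medical monitor approves | Differs on the exception only |

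The first reading fits Table 9's labels. Even the second leaves a difference.

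**Step 3. Whether letting specific text override general text removes the conflict.** Suppose each specific section displaces Table 10, and *severe* includes Grade 3. Then at Grade 3:

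| Event | Governing text | Instruction |
|---|---|---|
| Pneumonitis, enterocolitis, hepatitis, neuropathy | Tables 11, 12, 13, 15 | Discontinue, exceptions by medical-monitor approval |
| Dermatitis | Table 14 | Withhold, same-dose restart possible |
| Endocrinopathy | Table 16 | Withhold or discontinue, same-dose restart possible |
| All others | Section 5.4.5.7 | Permanent stop |

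Table 10's Grade 3 rule would then govern no class of event. If Table 10 does apply to the last row, it contradicts 5.4.5.7. Either way the texts are not aligned.

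**Step 4. Grade 4 dermatitis.** Tables 9 and 10 and Sections 5.4.8 and 5.5.1 agree: stop unless the medical monitor approves. Table 14 allows a same-dose restart of every drug after resolution to baseline within 4 weeks, with no approval step. Its only mention of the medical monitor concerns events unresolved at 6 weeks.

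**Step 5. Restart dose after Grade 3 (a lesser inconsistency).** Tables 9 and 10 lower epacadostat one level. Tables 14 and 16 allow the same dose. Cross-references in 5.4.4.2, in 5.4.5 and below Table 10 send the reader to the detailed sections, but none says which text prevails.

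**The case against.** The best defense is that the structure already signals how to read it. Tables 9 and 10 are titled as general guidelines, and the text points to the organ-specific sections for detail. A permissive restart and a mandatory withdrawal can both be respected by obtaining approval first. Section 5.4.5 asks for immediate discussion with the sponsor of any immune-related AE of Grade 2 or higher, and Section 5.4.4 asks for consultation with the medical monitor on interruption and reduction.

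Part of this stands. Specific over general is a reasonable reading of Tables 14 and 16 against Tables 9 and 10 on the Grade 3 restart dose, which is why that item is secondary. It does not settle the two main items. It leaves Table 10's Grade 3 rule without any event to govern, and it would let Table 14 displace Sections 5.4.8 and 5.5.1, which are worded as requirements. Discussion is also not approval, and a site working from Table 14 is not told that approval is needed.

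A reader might infer something stronger: four competing instructions for every Grade 3 or 4 immune-related AE. The documents do not support that. Section 5.4.5.7 is headed as covering other reactions, so it does not compete with Tables 14 and 16. Table 16 allows same-dose restart at Grade 3 only. The Grade 4 stop in 5.4.8 carries an approval exception.

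**Conclusion.** The point holds for two contradictions: Section 5.4.5.7 against Table 10 for severe reactions without their own table, and Table 14 against Tables 9 and 10 and Sections 5.4.8 and 5.5.1 for Grade 4 dermatitis. The first assumes that *severe* includes Grade 3, as Table 9's label indicates. The second needs no assumption about that word. For a subject who has stopped epacadostat under Amendment 2, the dose-reduction element falls away, but whether the antibodies may be resumed remains unclear.

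Its frequency cannot be stated, because the documents give neither the number of subjects still on treatment nor Grade 3 and 4 rates for this triplet. A reader might reach for the 10% and 15% rates of Grade 3 or higher rash in Section 1.4.4. Those come from epacadostat with nivolumab alone, the 15% is from a 300 mg BID dose not used here, and neither gives a Grade 4 rate. Renal events are not a safe example either: 5.4.5.7 refers them to Appendix B, whose renal algorithm is not visible in the text available.

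This should be corrected because opposite actions on the same event can each be justified from current text. It does not affect the sample size or the ORR analysis plan.

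**What to change.** 1. Reconcile Section 5.4.5.7 with Tables 9 and 10, and express *severe* in 5.4.5.7 as a CTCAE grade.
2. Reconcile the Grade 3 and 4 row of Table 14 with Tables 9 and 10 and with Sections 5.4.8 and 5.5.1, including whether the approval step applies.
3. Add one sentence saying which text governs when the general tables, the organ-specific tables and Section 5.4.8 differ. This would also settle the restart-dose difference between Tables 9 and 10 and Tables 14 and 16.

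Which clinical rule applies is for the sponsor to decide, and this point does not presuppose different rules for Grade 3 and Grade 4. The cost is wording changes in Section 5.4.5.7 and the affected tables plus one precedence sentence, with notice to sites that still have subjects on treatment. No new data collection or analysis is needed.

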5.4.4.1. Epacadostat Dose Modifications

[Table 8](#) describes epacadostat dose reductions that may occur due to any related AEs. Dose reductions should occur in a step-wise fashion from the initial starting dose of the cohort, and a maximum of 2 dose reductions of epacadostat are allowed for the management of an AE. If an AE recurs/does not return to baseline after the second dose reduction of epacadostat, then the subject must permanently discontinue epacadostat.

The lowest permissible dose of epacadostat is 25 mg BID. If a subject does not tolerate 25 mg BID, then the subject must permanently discontinue epacadostat. If epacadostat is discontinued after 2 dose reductions, or if a 25 mg BID dose is not tolerated, the subject may resume treatment with nivolumab monotherapy (or nivolumab with ipilimumab, if applicable) once criteria for restarting study treatment have been met with approval from the medical monitor.

Table 8: Dose Reductions of Epacadostat (Treatment Groups A and B)

Dose of Epacadostat	Dose Level -1	Dose Level -2
	First Reduction of Epacadostat	Second Reduction of Epacadostat
100 mg BID	50 mg BID	25 mg BID
50 mg BID	25 mg BID	N/A – Discontinue Treatment
25 mg BID	N/A – Discontinue Treatment	N/A – Discontinue Treatment

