5.4.4.2. Nivolumab, Ipilimumab, and Lirilumab Dose Modifications

There will be no dose reductions of nivolumab, ipilimumab, or lirilumab allowed for the management of toxicities of individual subjects. Doses of these agents are held for toxicity management, per Table 9. See Section 5.4.5 for dose modification and toxicity management guidelines pertaining to specific irAEs.

Table 9: General Guidelines for Interruption and Restarting of Study Treatment

CTCAE Grade/Severity	Hold Treatment (Y/N)	Timing for Restarting Treatment	Dose Level for Restarting Epacadostat	Dose Level for Restarting Nivolumab and Ipilimumab (Treatment Group A), or Nivolumab and Lirilumab (Treatment Group B)	Treatment Discontinuation
1-2 (Mild-moderate)	No	Continue treatment at the discretion of the investigator.	N/A – If held, restart at same dose.	NA - If held, restart at same dose.	N/A
3 ^a (Severe)	Yes	Toxicity resolves to Grade 0-1.	Reduce by 1 dose level. ^b	Restart same dose.	Toxicity does not resolve within 4 weeks (28 days) of last dose, except by approval of the medical monitor. OR Second occurrence of previously resolved Grade 3 AE.
4 ^c (Life-threatening)	Yes	Permanent discontinuation, except by approval of the medical monitor. If continuing, toxicity must resolve to Grade 0-1.	Permanent discontinuation, except by approval of the medical monitor. If continuing, reduce by 1 dose level. ^b	Permanent discontinuation, except by approval of the medical monitor. ^c If continuing, restart same dose.	Permanent discontinuation for any severe or life-threatening event, except by approval of the medical monitor.

^a Grade 3 amylase or lipase abnormalities that are not associated with symptoms or clinical manifestations of pancreatitis do not require a dose delay. It is recommended to consult with the medical monitor for Grade 3 amylase or lipase abnormalities.

^b See Table 8 for epacadostat dose reduction guidelines. See Section 5.4.8 for study treatment withdrawal criteria.

^c Isolated Grade 4 lipase or amylase abnormalities not associated with symptoms or clinical manifestations of pancreatitis may not require treatment discontinuation. Medical monitor should be consulted for any Grade 4 amylase or lipase abnormality.

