5.5. Withdrawal of Subjects From Study Treatment

5.5.1. Withdrawal Criteria

Subjects may withdraw consent at any time for any reason or be withdrawn from study treatment at the discretion of the investigator should any untoward effect occur. In addition, a subject may be withdrawn by the investigator or the sponsor if enrollment in the study is inappropriate, the study plan is violated, or for administrative and/or other safety reasons.

Subjects **must** be withdrawn from study treatment for the following reasons:

- The subject becomes pregnant.
- Consent is withdrawn. Subjects may choose to withdraw from the study at any time without penalty of jeopardizing their health care or loss of benefits to which the subject is otherwise entitled.
Note: Consent withdrawn means that the subject can no longer be followed and no additional data can be collected.
- Further participation would be injurious to the subject's health or well-being, in the investigator's medical judgment.
- Unacceptable toxicity (see Section 5.4.8). Subjects with unacceptable toxicities must be withdrawn from study treatment but will continue in the safety follow-up period of the study (see Section 6.4).
- The subject has received study treatment for 2 years (ie, 24 months have elapsed since Cycle 1 Day 1).
- The study is terminated by the sponsor.
- The study is terminated by the local health authority, IRB, or IEC.

A subject **may** be discontinued from study treatment as follows:

- Radiographic progression of disease per RECIST v1.1 (see [Appendix E](#)). A subject may continue on treatment after radiographic progression is confirmed per RECIST v1.1 if clinically stable or clinically improved, pending confirmation of disease progression [REDACTED] (see Sections [5.5.1.1](#) and [7.6.1](#)).
- If, during the course of the study, a subject is found not to have met eligibility criteria (see Section [3](#)), the medical monitor, in collaboration with the investigator, will determine whether the subject should be withdrawn from the study.
- If a subject is lost to follow-up or noncompliant with study procedures or study treatment in the investigator's opinion, the sponsor should be consulted for instruction on handling the subject.

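### A Grade 2 ocular immune-related event that responds to eye drops must end treatment under 5.4.8 and 5.5.1, but Tables 9 and 10 permit continuation and 5.4.5.7 does not carry the rule

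*Combined protocol and SAP*

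**What the plan says.** Section 5.4.8 defines unacceptable toxicity and says its occurrence "will require that the study drug be permanently discontinued". One listed item, set at or above the stated grade, is "Grade 2 ocular irAE". That item has no condition on response to therapy and no approval route. Two other items in the same list do have one: Grade 4 events (medical monitor approval) and long treatment delays (sponsor approval). Section 5.5.1 then puts unacceptable toxicity among the mandatory reasons for stopping: "Subjects with unacceptable toxicities must be withdrawn from study treatment".

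The management text reads differently.

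- **5.4.5.7** prescribes corticosteroid eye drops for uveitis, iritis and episcleritis, and then says: "All study treatment should be permanently discontinued for immune-mediated ocular disease that is unresponsive to local immunosuppressive therapy". It also stops treatment for severe immune-mediated reactions in general. It does not mention Grade 2 and does not cite 5.4.8.
- **Table 9 (5.4.4.2), Grade 1-2 row** answers No to holding treatment, says "Continue treatment at the discretion of the investigator", and marks treatment discontinuation as not applicable.
- **Table 10 (5.4.5), Grade 2 row** leaves holding to the investigator and allows restart at the same dose and schedule if the event resolves within 4 weeks.

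Neither row names an ocular exception. Section 5.4.4.2 also tells sites where to look: "See Section 5.4.5 for dose modification and toxicity management guidelines pertaining to specific irAEs".

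**The concern.** For one clinical event the protocol gives a mandatory permanent stop in two places and permission to continue or restart in two others. The section written for that event sets a different trigger and does not mention the mandatory one. The routing makes this worse: 5.4.4.2 and the note under Table 10 send sites to the 5.4.5 subsections, which is where the Grade 2 ocular stop is missing.

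What is at stake is a patient-safety stop for Treatment Group A subjects still on study treatment. Amendment 2 closes enrollment but keeps those subjects on therapy, so the rule can still be triggered. A site could continue or resume dosing in good faith after an event that should have ended treatment.

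**Working it through.** No arithmetic applies. The check takes one test case, a Grade 2 ocular irAE that responds to corticosteroid eye drops, and reads each rule for what it requires.

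| Text | Status | Outcome for the test case |
|---|---|---|
| 5.4.8, ocular item | Mandatory, no exception | Permanent discontinuation |
| 5.5.1 | Mandatory | Withdrawal from study treatment |
| 5.4.5.7, ocular sentence | Trigger is non-response | Trigger not met; silent on 5.4.8 |
| 5.4.5.7, severe reactions | Trigger is severity | Not met at Grade 2 |
| Table 9, Grade 1-2 row | General guideline | No hold; continue; discontinuation not applicable |
| Table 10, Grade 2 row | General guideline for irAEs | Hold optional; same-dose restart if resolved within 4 weeks |

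**Is the Grade 2 threshold deliberate?** Table 7 lists ocular irAEs of Grade 2 or higher as dose-limiting toxicities in Phase 1. The same threshold appears in two independent places, so 5.4.8 is unlikely to be a slip.

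**Do existing cross-references close the gap?** Only in part. The Table 10 Grade 2 row has a footnote pointing to 5.4.8, but it is attached to the epacadostat dose-reduction step for events lasting beyond 4 weeks, not to the optional hold or the same-dose restart. In Table 9 the footnote naming 5.4.8 is attached to the Grade 3 and Grade 4 rows, not to Grade 1-2.

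**Where does the conflict end?**

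- Grade 1: 5.4.8 does not apply, and the non-response trigger in 5.4.5.7 works alone.
- Grade 2, not responding: 5.4.5.7 and 5.4.8 agree on stopping.
- Grade 2, responding: 5.4.8 and 5.5.1 stop; the two table rows permit continuation; 5.4.5.7 gives no stop.
- Grade 3: Table 9 and the grading scale in 8.1.2 describe this as severe, so the severe-reaction sentence in 5.4.5.7 already stops treatment.
- Grade 4: Table 10 discontinues treatment.

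The discrepancy is therefore confined to one grade and, within it, to responsive events. Two table rows bear on it. The Appendix B algorithms are figures and could not be read; none of their seven headings is ocular.

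**The case against.** The strongest reply is that nothing strictly contradicts 5.4.8. A reader might infer that 5.4.5.7 lets responsive ocular disease continue. It does not say so: it never says *only*, and a site can satisfy both sections by stopping when either trigger is met. That part of the objection stands. As regards 5.4.5.7, the fault is an omission. Permission to continue comes from Tables 9 and 10.

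Those tables are general guidelines, and they omit other organ-specific stops too. The Table 10 Grade 3 row contemplates restart, yet pneumonitis, enterocolitis, hepatitis and neuropathy are discontinued at Grade 3 unless the medical monitor agrees otherwise. That is fair as a description of the layout. But in those four cases the subsection the site is sent to contains the stop. For a Grade 2 ocular event it does not.

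Two wider readings are tempting and should be resisted.

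- *The Grade 3 rows have the same defect.* They also lack an ocular exception, but 5.4.5.7 already stops severe reactions.
- *It is unclear which agents stop.* The body of 5.4.8 refers to the study drug in the singular. Section 5.4.4.1 also lets the antibodies resume after epacadostat is given up for another toxicity on the list ("Toxicity requiring more than 2 dose reductions of epacadostat, or dose reductions below 25 mg BID"). However, the 5.4.8 heading and 5.5.1 both refer to study treatment, which settles the scope, and 5.4.4.1 says nothing about ocular events.

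The objection that impact is small also stands. Section 5.4.5 says irAEs of Grade 2 or higher should be discussed with the sponsor immediately, so a site should not be deciding alone. That lowers the risk. It does not align the written rules, and the ocular item in 5.4.8 leaves no room for case-by-case approval.

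**Conclusion.** The stop rules for a responsive Grade 2 ocular irAE conflict as written, at low severity. On a careful reading 5.4.8 and 5.5.1 control, because they are mandatory and the tables are guidance. No explicit order of precedence is stated, however, and sites are directed to the laxer text.

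The documents give no frequency for such events, so the number of subjects affected cannot be estimated. Enrollment is closed, Treatment Group B enrolled nobody, and the sponsor-contact instruction is a real safeguard. Sample size, power, significance level and planned analyses are untouched. The conclusion assumes that the sponsor intends the Grade 2 threshold, which Table 7 supports, and that the Appendix B figures do not themselves state the ocular stop.

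**What to change.** 1. Add to 5.4.5.7: *Any Grade 2 or higher ocular irAE requires permanent discontinuation of study treatment per Section 5.4.8, whether or not it responds to local therapy. For Grade 1 ocular irAEs, discontinue if local immunosuppressive treatment fails.*
2. Add to the Table 9 Grade 1-2 row and the Table 10 Grade 2 row: *Except ocular irAEs of Grade 2 or higher: discontinue per Section 5.4.8.*

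No change to the Grade 3 rows is needed, and no clarification of which agents stop.

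The cost is two sentences and one short phrase in two rows. The clinical price is that subjects whose Grade 2 event is controlled by eye drops lose treatment, but 5.4.8 already requires that. If the sponsor would rather let such subjects continue, 5.4.8 itself has to be amended, because 5.5.1 does not allow it now.
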